Once generated, documents that include the randomization sequence will be password protected to avoid inadvertent access by research staff involved in the enrollment process. The treatment condition assignments will be sealed in envelopes according to the allocation sequence by either the project coordinator or the study data manager prior to the beginning of study recruitment. The randomization process will be overseen by our study data manager and the project coordinator will be notified of assigned condition for specific participants at the completion of all baseline assessments (by opening sealed envelopes). Randomization should occur at the baseline enrollment appointment. Initiation of the study treatment condition (either CBTI-CB or SHE) should take place within one week of study enrollment and randomization in order to provide enough time for all sessions to be completed within the 6-8-week treatment window.

Following randomization, the participants will be provided with an actigraph sleep monitoring watch if it is deemed safe by investigators and the University of Michigan Office of Research (UMOR). By “safe,” we mean that the risk of transmitting COVID-19 via the actigraphy watches or by going into the office to mail/pick up/configure watches is very low. This risk level is likely to change during the course of the study, and decisions will be made on a case by case basis at enrollment. Participants who are given the option to participate in actigraphy sleep data capture will have the option to decline and still participate in the full study. The actigraph (Actiwatch Spectrum Plus, Philips Respironics, Murrysville, PA) is a small waterproof device the size of wrist watch (48 mm x 37 mm x 15 mm weighing 31 grams) that is meant to be worn continuously on the non-dominant wrist. An accelerometer integrates movement frequency and intensity into a single measurement. In addition, a photodiode sensor continuously monitors incoming light and stores the data in lux levels. The actigraphs are set at a sampling rate of 30 seconds. Activity and light data are downloaded to computer and sleep/wake activity is estimated using Actiware® – Sleep software and following published guidelines. Data is accessed through the Actiware® – Sleep software and is identified by study participation ID. Participants will be asked to wear the actigraphy activity tracker for one-week (at least 7 consecutive days) post-enrollment, for at least one-week post-treatment (at approximately 8 weeks' post-enrollment), and at least one-week pre final follow up (at approximately 16 weeks' post-enrollment). Watches will be returned to the study team after the first 7 days of wear, returned to the participant after the last therapy session, collected by the study team at the follow up assessment, returned to the participant approximately 1 week before the final follow up assessment, and collected by the study team at that final assessment. To do so, we will ask participants to either 1. send the actigraphy activity tracker back in the mail using a prepaid envelope, 2. leave it in a drop box located at some of the recruitment sites, or 3. have study staff meet the participant at home or in the community to pick up or drop off the actigraphy activity tracker. Participants will be asked to wear the watch for at least 7 days post-treatment and again for at least 7 days pre- final follow up, and will return the watch at their in-person follow up or via mail after their electronic/mailed follow up is completed. Actigraphy activity trackers will come with informational brochures from the Philips Respironics company and pre-paid return envelopes for the participants to mail them back after both baseline and post-treatment assessment time points. Once the participant completes the survey, research staff will review the survey prior to the participant leaving the room to assess for risk status.

Follow-up assessments will be conducted in person in the community, in our offices at the University of Michigan, or via emails containing REDCap survey links or mailed paper surveys where participants can complete surveys on their own. For those assessments that occur in the community, research staff will arrange to meet participants at a convenient and confidential location in the community (e.g., a local library, their home). If we interview a participant in his/her home, we will arrange for a second research staff member to go along for staff safety reasons. We have used this process successfully in our prior work with adults with SUD. For surveys that are taken online, appointments will be scheduled with participants for research staff to contact

them via a video chat platform (BlueJeans, Skype for Business, or Zoom through the University of Michigan) or via phone to complete the TLFB interview.

Data Collection: Assessment content will measure demographic characteristics, reasons for seeking cannabis and current uses (must include insomnia), frequency and severity of insomnia, and presence of co-occurring exclusionary medical/psychiatric conditions, and other sleep disorders. The screening assessment will include questions that will allow for determination of eligibility. Baseline assessments are intended to confirm eligibility and collect data on participants' sleep, functioning, and substance use. Data will be collected via emailed surveys, tablets, paper, actigraphy, and urine drug screens.

Specimens: In this study, we will be collecting urine to analyze for recent cannabis and other illicit drug use. The urine drug screen will provide information regarding recent use for opioids, cannabis, amphetamines, methamphetamines, and cocaine. We will be using urine testing kits that give immediate results; therefore, the study staff will be conducting the sample testing and no labeling or storage will be necessary. Participants will be given a small bag containing the test kit to take into a restroom, either at the recruitment/follow up location or at home, or they will be mailed a urine drug screen to use at home. Once the specimen has been provided in the test cup, the participant will either return the bag to the research staff member for immediate testing or schedule an appointment with research staff using a video chat platform (BlueJeans, Skype for Business, or Zoom through the University of Michigan) to use the urine drug screen off camera and immediately share the results with research staff. A final option is for participants to send a picture of the results to the secure study email. Research staff will record test results. After testing is complete, the urine sample will be discarded by flushing it down the toilet if done in person. No identifying information will be marked on the testing container. The validity of self-report of cannabis use and other illicit drug use may be increased when a urine drug screen is performed. Specimens will be collected in a specimen container about 4 oz. in size, although only a minimal amount of urine is needed.

Assessment Instruments	Screening/ Eligibility	Baseline	Before and/or after session	Follow Up ~8 weeks	Follow Up ~16 weeks
Demographics	X				
Alcohol, Smoking and Substance Involvement Screening Test (ASSIST)	X				
Fagerstrom Test (for nicotine dependence)	X				
Fagerstrom Test (for cannabis dependence)	X				
Cannabis Use Disorder Identification Test (CUDIT)	X			X	X
Perceived Relief (PR)	X			X	X
STOP-BANG (Obstructive Sleep Apnea measure)	X				
Restless Leg Syndrome Questionnaire (RLSQ)	X				
Insomnia Severity Index (ISI)	X			X	X
Morningness/Eveningness Questionnaire		X			

Urine Drug Screen	X			X	X
Personal Health Questionnaire Depression Scale (PHQ-8)		X		X	X
12-Item Short Form Health Survey (SF-12)		X		X	X
Timeline Follow Back		X		X	X
Modified Self Efficacy Scale (SES)		X		X	X
Dysfunctional Beliefs About Sleep (DBAS-16)		X		X	X
Substance Use Sleep Scale (SUSS)		X		X	X
Modified Marijuana Motives Questionnaire (MMQ)		X			
Medical Marijuana Use		X			
Prescription Misuse (BOYD)		X		X	X
Side Effect Checklist (SECL)		X		X	X
Marijuana withdrawal checklist revised (MWC-R)		X		X	X
PEG Three-item Scale Assessing Pain Intensity and Interference		X		X	X
BRFSS Model 16(Marijuana Use Type)		X		X	X
Multidimensional Fatigue Inventory (MFI-20)		X		X	X
Epworth Sleepiness Scale		X		X	X
Therapy Evaluation Questionnaire		X		X	
Working Alliance Inventory-SR				X	
Daily Sleep/Wake Diary		X	X	X	X
Actigraphy		X		X	X
Session Attendance			X	X	

Primary outcomes: The ultimate goal is to use this pilot study to provide all of the necessary elements to conduct a future fully-powered RCT comparing these two conditions. We hope to assess the acceptability and feasibility of RCT procedures to determine the distribution and variability of the primary outcomes (insomnia

severity). This will be measured by the change from baseline Insomnia Severity Index score to the score at study completion.

All remuneration for the study will be in the form of gift cards or cash. Participants will be remunerated with a \$40 for the completion of baseline assessment, \$40 for completion of each follow-up assessment, \$20 for completing four out of seven days of the daily online survey for every week before the first follow up and \$10 for completing four out of seven days of the daily online survey for the week before the 2nd follow up, plus an additional \$10 incentive for a urine drug screen at both follow ups. Participants will also receive \$30 to compensate them for any potential charges related to the use of their technology. Participants who do not complete all therapy sessions will still receive the \$30 to cover technology costs, however, they must have completed at least one phone session.

Informed consent. A two-level consent procedure will be used in this study. At screening and baseline, participants will be asked to provide informed consent. After screening, those eligible will be asked to complete a second consent. To enhance confidentiality and minimize the collection of identifying information about individuals who do not participate in the study, screening consent will be administered online (a waiver of documentation of informed consent for screening is requested) or on study provided tablet computers as the first page of the screening survey. Prospective participants that use the online screening process will enter the survey portal from a link provided in the recruitment ad (paper or electronic) directing them to the UMHealthResearch.org site, where a link for the survey will be available. After clicking the survey link, they will then be asked to review and sign an e-consent to the short screening survey. During initiation of the screening survey each participant will be assigned a unique respondent ID number by REDCap. Participants will give consent by checking a box on the electronic consent form and will self-administer a screening survey. In the event of technological issues with study tablets or internet service, or participant preference, verbal consent may be obtained for screening and paper/pencil surveys completed. Following determination of eligibility, negative screens will receive a thank you page asking for a phone number or email address to be sent their gift card and ending their participation. The only identifying information collected from those who complete the screen and are ineligible or choose not to participate in the study will be an email address or phone number, to text or email Amazon gift card codes for screening assessment remuneration. Eligible participants will be asked to provide their name, email address, and phone number for scheduling purposes. Study staff will reach out to eligible participants to schedule the urine drug screen and baseline assessment.

For those eligible based on screening responses and interested in participating in the full study, written or verbal informed consent for the full study will be obtained. Individuals interested in participating in the study will review the consent that will be emailed, texted or handed to them with the research staff in person or via a video chat platform (BlueJeans, Skype for Business, or Zoom through the University of Michigan). All participants will be told that participation is voluntary, that they can withdraw at any time, and that this will not impact any aspect of the services they receive at the clinics or dispensaries, including their ability to receive cannabis (if recruited from dispensaries). After reviewing the consent form, research staff will ask the patient if he/she has any questions regarding their participation or the study requirements and limitations. The limits of the Certificate of Confidentiality are explained in the consent form, but study staff will also verbally explain the limits of confidentiality. Any patients who request more time to review the consent form or consult with others will have the opportunity to do so. These patients will have the opportunity to have research staff contact them at a later time or to contact research staff themselves. Those interested in participating will be asked to consent to the research project. When providing informed consent, participants will be given, mailed or emailed a copy of the consent form to keep and the original will be filed in a confidential research file or study staff will record the date, time, and research staff conducting the consent in the secure database. Study staff will review the consent form for accuracy and completeness before beginning any study procedures. RAs will fully review the consent document, answer all questions and provide a copy of the consent document to the participant. All consent information will be filed in a confidential research database.

Study Eligibility Criteria.

Inclusion criteria. (1) age > 21 or older; (2) Insomnia Severity Index (ISI) score >10, indicative of at least “mild” insomnia; (3) use of cannabis three times a week within the past three months; (4) self-reported use of cannabis to manage insomnia at least once a week over the past month; (5) consistent access to a telephone, smartphone, laptop, or tablet; and (6) a positive urine drug screen for THC.

Exclusion criteria. (1) individuals who do not understand English; (2) individuals judged unable to provide informed consent (e.g., intoxication, mental incompetence, psychosis, bipolar disorder); (3) diagnosis or high suspicion of a sleep disorder other than insomnia based on validated self-report measures; (4) self-reported cancer; (5) self-reported pregnancy; (6) self-reported rotating or night (3rd) shift work; (7) resides a distance greater than 50 miles from Ann Arbor. Participants will not be excluded if they are taking prescription or over the counter medications for sleep, however they will need to report being stable on the medications for at least 8 weeks and agree to maintain the same regime throughout the study. Those who have been taking prescription medications for sleep for less than 8 weeks, or who report they are unable to continue with their medications for the duration of the study (approximately 16-18 weeks) will be excluded.

Research staff will use their clinical judgment to assess cognitive ability to consent. If necessary, recruitment staff may require a potential participant to pass a brief mental status exam. Potential participants may be excluded based on participant best interest (e.g., adult patient with a legal guardian; or if study staff know a patient or their family personally, in order to fully ensure participant privacy), with PI approval.

Justification for selection criteria. Participants in this study will be 21 years old and older for several reasons. First, although state law does allow individuals under the age of 18 to obtain cannabis for medical purposes with consent of a legal guardian, available data indicate that very few adolescents have been issued medical cannabis cards in Michigan. In addition, with the new recreational marijuana laws allowing non-medical use of cannabis, we are not solely recruiting medical cannabis users. This new law states all recreational marijuana uses must be 21 years or older to possess or use marijuana. Therefore, all participants should be age 21 years or older to follow Michigan recreational marijuana laws.

In order to collect interview data from a sample that will be representative of the population to be recruited for the RCT, we will exclude those with self-reported cancer or pregnancy. Individuals who use marijuana for cancer may experience a different trajectory than those who are not and women who self-report that they are pregnant will be excluded because: (a) of the potential risks of study participation to pregnant women; and (b) we are unlikely to have sufficient numbers of pregnant women to facilitate meaningful subgroup analyses.

Access to a smartphone, computer, or tablet is required to deliver intervention sessions, as all sessions are meant to be delivered remotely via BlueJeans video chat or telephone. Those who do not report having reasonable access to the technology needed for the study will be excluded.

Potential Risks, Minimizing Risks, and Potential Benefits

1. Potential Risks
 - a. Loss of Confidentiality

The major potential risk to study participants is violation of confidentiality of survey and interview data. The risk of violation of confidentiality exists because participants will be disclosing personal information in surveys and interviews. This risk is related to the damage that could be caused by an inadvertent release of sensitive information (e.g., substance use, medical conditions). Participants will be informed of the procedures taken to protect their confidentiality.

b. Discomfort During Interview

There is also a slight risk of psychological discomfort to study participants as a result of being asked personal questions on sensitive topics. Participants may also become anxious or upset during discussions of their thoughts about managing their insomnia or substance use during the interview.

2. Minimizing risk

a. Loss of confidentiality (risk unlikely)

To minimize the violation of confidentiality, we will ensure that data are protected and cannot be linked to a particular person. Unique identification numbers will be assigned to each participant and all forms are coded with this number, rather than by name. All data are stored in locked file cabinets. Consent forms and subject code/name sheets will be stored separately, because they contain identifying information. Data entry staff will work with forms that contain only subject numbers. Physical security of data will be assured by daily and weekly back-ups. Data cleaning will be conducted throughout the data collection period to ensure the production of a final dataset for analysis at the end of data collection.

Study data will be collected and managed using REDCap (Research Electronic Data Capture). Participants' names and contact information will be stored in a secure, REDCap database, separate from their study data and only accessible to members of the research team for research purposes. REDCap is a secure web application designed to support data capture for research studies. It provides userfriendly web-based case report forms, real-time data entry with branching logic and validation (e.g. for data types and range checks), audit trails, a de-identified data export mechanism to common statistical packages (SPSS, SAS, Stata, R/S-Plus), procedures for importing data from external sources, and advanced features such as a data quality check module. The system was developed by a multiinstitutional consortium initiated at Vanderbilt University. REDCap servers are physically located in the University of Michigan Medical School Information Systems (MSIS) data center. Application and database servers are on virtual machines (VM). The VM servers are Red Hat Enterprise Linux Server 5.6 (64-bit, 2.6.18 238 e15-smp kernel) 2x AMD Opteron 6174 5.0.95 2.2 GHz with 4 GB RAM, running Apache 2.2.3 (application servers) and MySQL (database servers). Physical security for the databases is provided in a professionally managed and equipped tier-2 data center with tightly controlled access. Remote data access employs SSL encryption and 2-tier Kerberos/Level 1 and UMHS Level 2 password challenges via LDAP authentication. Access to the application, the database, and the underlying systems infrastructure are consistent with industry best practices including HIPAA security and privacy requirements and the HITECH Act. The applicationprovides audit trails on user access to MICHRS and MSIS technical and support teams. Backup of data is managed by MSIS and vulnerability testing is performed regularly by the University of Michigan Health

System Medical Center Information Technology. Risk evaluation is performed using a methodology derived from NIST Special Publication 800-53 – “Recommended Security Controls for Federal Information Systems” and is used to refine and improve operating policies and procedures. Daily backups and VM snapshots of the application and database servers are stored on a remote storage device. The restoration of the servers from a hardware or software failure are protected for 24 hours of disaster recovery.

To test a new participant tracking program, participant personal information will also be kept in Ripple™, a secure web application designed for the storing and management of personally identifying information of research participants. Ripple was initially developed at the University of Michigan to provide a user-friendly, web-based secure interface where research teams can centralize the storage and management of research participants' personal information, including name, participant ID, demographics, and study workflow (e.g., appointments). Participant information managed with ripple is private and secure. This information is kept in

fully encrypted format inside dedicated databases that are segregated from other Ripple accounts and thus only authorized study staff will have access to the study data. Likewise, Ripple infrastructure complies with the privacy and security guidelines of the Health Insurance Portability and Accountability Act (HIPAA), including 2048-bit data encryption in transit and at rest, automatic logoff, audit trail, daily backups in triplicate dedicated servers, firewall, custom access permission for lab members, zxcvbn password strength estimation, and enterprise administrative safeguards to prevent unauthorized staff from accessing participant information. Furthermore, Ripple is used only for storing personally identifiable information of participants and is not used to capture other research data (e.g., questionnaires, health records, etc.). This ensures that the personally identifiable information and research data are segregated. As this is a pilot program, Ripple is only available to us for approximately 6 months of use. To avoid any data loss, participant tracking information will also be kept in REDCap, as mentioned above and as previously done in the beta testing phase of this project.

Interviews will be audio-recorded with participant permission for fidelity and may take place in person, via an online video chat (BlueJeans), or over the phone. The intervention sessions may be remotely delivered via telephone or BlueJeans video conferencing (<https://www.bluejeans.com/>). BlueJeans provides a cloud-based audio/video/content-sharing conferencing service. The service is vendor-agnostic and allows up to 150 endpoints to connect for a meeting. U-M's current contract with BlueJeans enables all U-M faculty, staff, and students to register for a BlueJeans User Account. BlueJeans collects and maintains data related to the date, time, and attendees of a meeting. Actual video or audio content is only stored by BlueJeans when the meeting host turns on the recording feature. We will not be using the recording feature on Bluejeans. U-M's agreement with BlueJeans includes a Business Associate Agreement. This means individuals may use this service to share Protected Health Information (PHI) regulated by HIPAA. For more information, BlueJeans Security and Privacy agreements with the University of Michigan can be found at <https://safecomputing.umich.edu/dataguide/?q=node/181>. The audio recordings for the interviews will be done with a digital voice recorder. The audio-recordings of the interviews will be destroyed after the files are uploaded to a password-protected, secure server with restricted access. Participants will be asked not to mention names or other identifying information in during the recorded interview. Due to an increase in use in the BlueJeans platform during the COVID-19 pandemic, we are also including the ability for research staff to use alternate video platforms approved by the University of Michigan, including Skype for Business, or Zoom through the University of Michigan.

We have set up an email account to be used for subjects to contact study staff or for study staff to send appointment reminders and online surveys (via REDCap) to subjects. The e-mail address is: [contact].

b) Discomfort during assessments (risk likely):

Participants may become upset, anxious, or uncomfortable as a result of being asked very personal questions. To minimize this risk, all interviews will be conducted in private offices with skilled research staff. Research assistants will be trained to respond to this emotional distress and to refer participants to appropriate resources as necessary. Specifically, this training will include information regarding evaluating warning signs of distress that could occur as a result of the screening, intervention, or assessments, and means of addressing such issues and minimizing distress. Such strategies will include maintaining an empathic response, acknowledging the distress through reflection, avoiding blame, processing in a non-blaming non-confrontational manner, and eliciting or encouraging use of relaxation and cognitive calming strategies. Crisis procedures, effective in previous projects conducted by the study investigators, will also be utilized, including immediately paging Drs. [name] or [name] (Multiple PIs) for consultation. If any research staff observes any indication of potential distress, including through review of responses to the assessments, further evaluation of the participant will be conducted by a licensed clinician. All participants are free to terminate the interview at any time or refuse to respond to any question. As with any research project, unexpected events are always possible. If risk is

determined to be present, we will implement our standard clinical protocol for responding to suicide risk, including giving participants a resource brochure. Ongoing follow-up will occur until it is determined that risk is minimal.

3. Potential Benefits of the Proposed Research to Human Subjects and Others

It is believed that research participants may be helped by participating in this study. Participants who receive the CBTi-CB intervention will receive a therapeutic intervention aimed to improve their insomnia symptoms and related functioning during the day. CBT for insomnia has known risks associated with its use, but these are usually tolerable and subjects may not otherwise receive treatment for insomnia. Thus, the risks associated with participating are reasonable in light of the potential benefits to the participating subjects and others. The information control condition represents an increased (enhanced) level of care from standard medical cannabis treatment provided at clinics.

4. Importance of the Knowledge to be Gained

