Developing training protocols for therapists. During the initial phases of the project, we will also refine our therapist training protocols. Therapist training will be led by [name] and the project coordinator. [name] is accredited in Behavioral Sleep Medicine and served as a consultant on the national Veteran's Administration cognitive-behavioral therapy for insomnia training program; thus, she is very experienced in training therapists in CBTi. Therapists will be required to review training manuals in CBTi (e.g., Insomnia: A Clinical Guide to Assessment and Treatment⁷⁸, Cognitive-Behavioral Therapy for Insomnia: A Session by Session Guide⁷⁹) as well as the study-specific therapist manuals. Skills training will follow both current CBTi dissemination protocols⁸⁰ as well as past experience by the research team, will include activities such as listening to de-identified tapes from prior research protocols demonstrating the therapeutic techniques, role playing, being directly observed by [name] while providing CBTi-CB to mock cases and during beta testing. The therapist will also receive training on how to handle potential crisis situations and adverse events. Two masters level therapists will be trained to deliver both interventions (CBTi-CB and SE).

Develop CBTi-CB and SE Integrity and Fidelity measures. With participant permission (>90% in previous work), all therapy sessions will be audio recorded to ensure therapist fidelity to the intervention manuals. The development of the integrity measures will be based on procedures used in Project MATCH⁸¹ and the prior experience of our research group. For each session topic, dichotomous items for therapist adherence will be generated from session outlines and materials to include specific session topics covered. This will produce 6 session-specific *Adherence Rating Scales* for each condition. To produce a *Therapist Skill/Competence Scale* to apply across sessions, Likert items covering general CBTi (e.g., delivery of session rationale in CBTi framework, skill teaching, in session CBTi exercises) therapist behaviors will be generated based on Cognitive Therapy Rating Scale (CTS). Instructions regarding item intent, examples and scoring guidelines will be developed for the Session-Specific Adherence Rating Scales, as well as the Therapist Skill/Competence Scale.

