Consistent with Stage 1B research, the primary goals for the pilot RCT are to obtain information about the feasibility of the proposed RCT and estimate the distribution and variability of primary and potential mechanistic outcomes within intervention and control conditions. Initial analyses will involve calculating the attrition rates for 6- and 18-week follow-up assessments in each study group and identifying predictors of drop-out. We will also quantify session attendance and note the percent of participants who did not complete all sessions to identify ways to decrease drop-out and non-compliance to the intervention. Additionally, we will examine all participant feedback from the *Session Feedback Forms* and descriptive data from the measures of treatment integrity and therapist fidelity measures. To examine treatment integrity and fidelity (*the Session-Specific Adherence Rating Scales* and the *Therapist Skill/Competence scale*), inter-rater reliability will be examined with Yule’s Y statistic, by contrasting therapist results with those of the raters, as well as by contrasting those of the two independent raters. The items will be summed to produce overall competency summary scales. Cronbach’s alpha will be used to examine the internal consistency of each summary scale separately for the therapist and raters. The items and rating scales (anchors) will be further refined (added, eliminated or modified), if necessary, based on discussion of face validity and analysis of item appropriateness. These items will be used to monitor therapist skill and fidelity to the intervention protocol and to maintain the integrity of the intervention.

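### Yule's Y, the only inter-rater statistic named for both fidelity scales, cannot be computed for the Likert competence items, and no inter-rater statistic is specified for the summed competency scores

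*Combined protocol and SAP*

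**What the plan says.** The section on developing the integrity and fidelity measures (Specific Aim 1) sets up two kinds of item. For adherence, "dichotomous items for therapist adherence will be generated from session outlines and materials". For the Therapist Skill/Competence Scale, "Likert items covering general CBTi (e.g., delivery of session rationale in CBTi framework, skill teaching, in session CBTi exercises) therapist behaviors will be generated". The number of scale points is not given.

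Just before the Data Analysis text of Specific Aim 2, the plan adds a scale of contaminating therapist behaviours. It is one component of competence for CBTi-CB and the primary competence measure for SE; its response format is not stated. The same paragraph has a quarter of session tapes double-coded on both scales.

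The Data Analysis text then names both instruments and states that "inter-rater reliability will be examined with Yule’s Y statistic". Two contrasts are planned: therapist against rater, and rater against rater. Next, "The items will be summed to produce overall competency summary scales". The one statistic named for those sums is Cronbach's alpha, which "will be used to examine the internal consistency of each summary scale separately for the therapist and raters".

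**The concern.** A single coefficient is assigned to two instruments whose items have different formats. It fits one of them. For the other, an analyst following the text could not produce the stated result without first inventing a rule for collapsing the Likert categories.

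What is at stake is the evidence that CBTi-CB was delivered with consistent, measurable skill. The pilot intends to use these items to monitor therapist skill and fidelity, and it is meant to supply the elements of a later full trial. As written, the double-coding would yield no agreement figure for the Likert competence items, and none is planned for the summed scores. The plan also promises "descriptive data from the measures of treatment integrity and therapist fidelity measures". Those could show that one rater scores higher on average, but they do not measure agreement tape by tape.

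**Working it through.** The plan states no reliability target or figure on this point, so there is nothing to reproduce. The check is one of definition, followed by an illustration of why an unstated cut-point matters.

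**1. Definition.** For a 2x2 table with cells a (yes-yes), b (yes-no), c (no-yes) and d (no-no),

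Y = (√(ad) − √(bc)) / (√(ad) + √(bc)).

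It has no form for a k x k table with k > 2, or for a multi-valued score.

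**2. Item formats against that definition.**
- Adherence items, dichotomous: computable. For example, cells 40, 5, 5, 40 give (40 − 5)/(40 + 5) = 0.78.
- General CBTi competence items, Likert: two raters give a k x k table with k > 2. Y is undefined until a cut-point is chosen, and none is stated.
- Contaminating-behaviour items: format not stated, so nothing can be concluded.
- Summed competency scores: the plan does not say that Y, or any other inter-rater statistic, will be run on them.

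**3. Does alpha fill the gap for the sums?** No. Alpha uses only the variances and covariances of the items within one source. If one rater scored every item exactly one point below the other, the two alphas would be identical although the raters never agreed.

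**4. Does the cut-point matter?** This is an illustration only. The 5 points, the latent correlation of 0.7 between raters, and category boundaries at −2, −1.2, −0.3 and 0.8 SD are all assumed. Two sets of 45 tapes were simulated:

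| Cut | Population Y | Set 1 cells (a, b, c, d) | Set 1 Y | Set 2 cells | Set 2 Y |
|---|---|---|---|---|---|
| ≥2 | 0.69 | 44, 1, 0, 0 | undefined (0/0) | 42, 1, 1, 1 | 0.73 |
| ≥3 | 0.57 | 41, 2, 1, 1 | 0.64 | 38, 2, 1, 4 | 0.79 |
| ≥4 | 0.50 | 25, 3, 7, 10 | 0.55 | 18, 7, 6, 14 | 0.42 |
| ≥5 | 0.53 | 5, 4, 2, 34 | 0.64 | 3, 3, 5, 34 | 0.45 |

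Set 1 at ≥4, for instance: (√250 − √21)/(√250 + √21) = (15.81 − 4.58)/(15.81 + 4.58) = 0.55. The same ratings give one value each without any cut: quadratic-weighted kappa 0.64 and 0.68, and ICC(2,1) 0.65 and 0.69.

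**5. How much data.** The RCT has 60 participants and six sessions each, with 25% of tapes double-coded: 60 x 6 x 0.25 = 90 tapes, of which 30 x 6 x 0.25 = 45 are CBTi-CB. This assumes full attendance and recording, and an even split of double-coding between arms. It describes the rater-rater contrast only; the therapist-rater contrast may draw on other coded tapes.

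**The case against.** The best defence is that the instruments do not exist yet. Items and scoring guidelines are still to be developed, and those guidelines could supply a cut-point. The ratings would also still be there, so a suitable coefficient could be computed later. Both are fair and keep the point small. But the plan does not say that a cut-point will be set, and the illustration shows that a choice made after seeing the data could move the result. The general reference to bivariate measures of association in the same Data Analysis text is not tied to rater reliability.

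Four stronger readings are tempting, and the documents do not support them.

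- *That the plan applies Y to the summed scores and fails there.* It never says so. For the sums, the accurate statement is that no inter-rater statistic is specified.
- *That Y is wrong for the adherence items because it measures association rather than agreement.* Y is computable there, and Y versus kappa or percent agreement is a choice of coefficient. The reference list includes a paper whose title compares these three, which suggests a deliberate choice, although the analysis text carries no citation marker.
- *That Y will usually break down on zero cells.* This depends on whether it is computed per item or pooled, on the number of items and on rater accuracy, none of which is stated. With prevalence 0.5 to 0.9 and accuracy 0.8 to 0.9 assumed, Y is 1 despite a disagreement, −1 or undefined in 54–77% of items at 7 tapes, but in only 0.1–4% when pooled to 45 independent ratings. At accuracy 0.95 the pooled figure is back to about 20% at prevalence 0.5 and 0.9.
- *That item refinement hangs on Y.* The plan bases refinement on discussion of face validity and on item appropriateness, with no reliability threshold.

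**Conclusion.** The point holds for the Likert competence items: the stated statistic does not fit the stated item format, and no cut-point bridges the two. That is a matter of definition and needs no numerical assumption. For the summed competency scores the finding is narrower: no inter-rater statistic is specified, and alpha does not stand in for one. The dichotomous adherence items are not affected, and no defect is claimed for the contaminating-behaviour items.

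Severity is minor. Only the fidelity evidence suffers; no outcome, sample size, treatment comparison or decision rule uses Y. The simulated values show only that an unstated cut-point can matter; they do not predict what this trial will find.

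**What to change.** In the fidelity paragraph of the Specific Aim 2 Data Analysis text, tie the statistic to the item format:

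- keep Yule's Y for dichotomous items;
- for the Likert competence items, name weighted kappa (with its weights) or an absolute-agreement ICC (with its model);
- for the summed competency scores, name the same ICC;
- state that each applies to both the therapist-rater and the rater-rater contrast.

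Wording by format will also cover the contaminating-behaviour items once their format is set. Cronbach's alpha can stay as the internal-consistency measure.

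The cost is a sentence or two and a little more analysis on ratings already planned, with no new recordings or coding.
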